D	dMAb AZD5396 and dMAb AZD8076	Day 0, 3	6 (3+3)	2x (0.25 mg dMAb AZD5396) + 2x (0.25 mg dMAb AZD8076)	34U	0.25 mL	OpBlock 0078	0.5 mg dMAb AZD5396 + 0.5 mg dMAb AZD8076
E	dMAb AZD5396 and dMAb AZD8076	Day 0, 3	5	2x (2 mg dMAb AZD5396) + 2x (2 mg dMAb AZD8076)	75U (0.5 mL)	0.70 mL	OpBlock 0078	4 mg dMAb AZD5396 + 4 mg dMAb AZD8076
F	dMAb AZD5396 and dMAb AZD8076	Day 0, 3	5	2x (0.5 mg dMAb AZD5396) + 2x (0.5 mg dMAb AZD8076)	75U (0.5 mL)	0.55 mL	OpBlock 0070	1 mg dMAb AZD5396 + 1 mg dMAb AZD8076
G	dMAb AZD5396 and dMAb AZD8076	Day 0, 3, 28, 31	5	4x (0.5 mg dMAb AZD5396) + 4x (0.5 mg dMAb AZD8076)	75U (0.5 mL)	0.55 mL	OpBlock 0078	2 mg dMAb AZD5396 + 2 mg dMAb AZD8076
	TOTAL		44-50^d					

^a All subjects will receive the study product by IM route of administration. All doses of optimized dMAb AZD5396 and dMAb AZD8076 will be prepared with Hylenex® less than 4 hours before dosing of subjects. Doses of Hylenex will vary depending on the cohort to allow for a different volume per injection

^b Use of CELLECTRA™ 2000 with Side Port needle, OpBlock 0078 and 5P-IM Side Port Array or Profusion Therapeutic Infusion needle (G47574) for Cohorts A-E & G.

^c Use of CELLECTRA™ 2000 with Side Port needle, OpBlock 0070 and 5P-IM Side Port Array for Cohort F.

^d Note that the n is defined as evaluable participants. Due to partial doses or early dropouts, we may dose up to 50 participants total to reach enough evaluable participants in each cohort. See Protocol section [8.2](#) which describes replacing participants.

The decision to open new cohorts in the clinical trial is justified by several key factors. Firstly, ensuring safety is of utmost importance in any clinical trial. By introducing additional cohorts, we will gather more data on the safety profile of the investigational product.

Secondly, evaluating the levels of expression of dMAbs is crucial for assessing the efficacy of this approach. The expression levels directly impact the therapeutic potency and effectiveness *in vivo*. By expanding the cohorts, we will gather a larger sample size and thereby obtain more reliable data on the expression levels of dMAbs in different individuals. This broader understanding of expression levels will aid in determining optimal dosages and predicting the treatment's potential success.

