7.2 Dosing and Follow-Up Evaluations

Once eligibility has been confirmed, the participant will be assigned to receive Investigational product. Visit dates and windows must be calculated from Day 0.

7.3 Day 0, Day 3, Day 28, and Day 31

The following evaluations will be performed on Day 0 (all cohorts), Day 3 (cohorts B-G), Day 28 (cohort G), and Day 31 (cohort G) only prior to Investigational product administration:

- Collect all present and/or new or ongoing adverse events (including history of new COVID 19 diagnosis).
- Document any present conditions and concomitant illnesses.
- Record current concomitant medications/treatments.
- Targeted physical examination (driven by symptoms).
- Record vital signs pre injection including heart rate (HR), respiratory rate (RR), blood pressure (BP), oral temperature.
- Collect urine for urinalysis and urine pregnancy test (if WOCBP).
- Collect blood for PT(INR) and aPTT, CBC with differential, serum chemistry, CPK.
- Collect serum for mAb AZD5396 and mAb AZD8076 level assessment and ADA evaluation.
- Provide Memory Aid.

Investigational product administration should occur after all the above pre-dose procedures have been completed.

Participants will receive two injections into the arm (deltoid)/leg (quadriceps) region at day 0 (all groups), and on day 3. Injections will be separated by ~30 minutes. Injections may be given in different arms or in an arm (deltoid) and a leg (quadriceps). If preferred or needed both doses can be done in the deltoid region or the lateral quadriceps, although the injections should be in different areas separated by at least 2 cm. The Day 3 injections may repeat an area already used on Day 0 as long as separated by at least 2 cm. For Cohort G, the Day 28 injections may be repeated in an area already used, and the Day 31 injections may repeat an area already used on Day 28 as long as separated by at least 2 cm.

If a participant has a DLT, as outlined in the protocol, the second dose of the product will not be given.

The following evaluations will be performed on Day 0 (all cohorts), Day 3 (cohorts B-G), Day 28 (cohort G), and Day 31 (cohort G) after Investigational product administration:

- Conduct targeted injection site reaction systemic and local assessments 30 min post each injection.
- Record vital signs post each injection including heart rate (HR), respiratory rate (RR), blood pressure (BP), oral temperature. Participants will be observed for 1 hour after the last injection.

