8.2 Participant Discontinuation/Withdrawal from the Study

Participants are free to withdraw from participation in the study at any time upon request. An investigator may discontinue or withdraw a participant from the study for the following reasons:

- Pregnancy
- If any clinical adverse event (AE), laboratory abnormality, or other medical condition or situation occurs such that continued participation in the study would not be in the best interest of the participant
- Disease progression which requires discontinuation of the study intervention
- If the participant meets an exclusion criterion (either newly developed or not previously recognized) that precludes further study participation

The reason for participant discontinuation or withdrawal from the study will be recorded on the Case Report Form (CRF). Subjects who sign the informed consent form and are scheduled for Day 0 but do not receive the study drug may be replaced. Subjects who sign the informed consent form and receive the study intervention, and subsequently withdraw, or are withdrawn or discontinued from the study, will be replaced at the discretion of the Investigator. Subjects in cohorts B, C, D, E, and F may be replaced if they do not receive both the Day 0 and the Day 3 doses. Subjects in cohort G may be replaced if they do not receive all four of the Day 0, 3, 28, and 31 doses. Subjects in these cohorts who

only receive Day 0 doses and want to continue in the study will be included in the A1 or A2 group for analysis.

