11.2 Analytical Populations

Analysis populations include:

- The safety analysis set includes all participants who receive at least one Investigational Product administration and for whom post-dose safety data are available. Participants will be analyzed as to the dose level and cohort they were enrolled in.
- The per-protocol (PP) analysis set comprises all participants who receive all planned Investigational product administration over all planned dosing visits, have no important protocol deviations, and have valid pharmacokinetic endpoint data available until Week 48. These will be documented and tabulated prior to database lock. Participants in this sample will be analyzed as to the administration regimen to which they were enrolled.
- The modified intention-to-treat (mITT) analysis set includes all participants who receive at least one Investigational product administration and have valid pharmacokinetic endpoint data available until Week 48. Participants in this sample will be analyzed as to the dose level to which they were assigned. Analyses on the mITT sample will be considered supportive of the corresponding PP analyses.

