11.3.6 Missing Values

The study is small, and we will be replacing subjects who do not receive medication per Investigator discretion. Subjects in cohorts B, C, D, E, and F may be replaced if they do not receive both the Day 0 and the Day 3 doses. Subjects in cohort G may be replaced if they do not receive all four of the Day 0, 3, 28, and 31 doses. Subjects in these cohorts who only receive Day 0 doses and want to continue in the study will be included in the A1 or A2 group for analysis. We do not anticipate employing methods for missing data and will report summaries from reported values.

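### Regrouping Day-0-only participants of Cohorts B to G into A1 or A2 contradicts the as-enrolled safety analysis and can remove a DLT from its own cohort's table

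*Protocol*

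**What the plan says.** Two sections regroup participants of Cohorts B to G who stop after Day 0 and stay in the study. Section 8.2 says that those who "only receive Day 0 doses and want to continue in the study will be included in the A1 or A2 group for analysis", and Section 11.3.6, under missing values, says again that they "will be included in the A1 or A2 group for analysis". Neither limits this to pharmacokinetics, and neither exempts safety data or DLTs.

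The same sections allow replacement. Participants in Cohorts B to F "may be replaced if they do not receive both the Day 0 and the Day 3 doses", and for the four-dose cohort: "Subjects in cohort G may be replaced if they do not receive all four of the Day 0, 3, 28, and 31 doses". Note d to Table 2 in Section 4.1 defines each cohort's n as evaluable participants and adds: "Due to partial doses or early dropouts, we may dose up to 50 participants total to reach enough evaluable participants in each cohort".

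Section 7.3 gives one route to a Day-0-only record: "If a participant has a DLT, as outlined in the protocol, the second dose of the product will not be given".

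Other sections point the other way. For the safety set, Section 11.2 says: "Participants will be analyzed as to the dose level and cohort they were enrolled in". It analyses the mITT set by assigned dose level. Section 4.2 counts DLTs within the cohort of enrolment: one in the first three enrolled brings an ad hoc DSMB review, and more than one in six means the dose is not tolerated.

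**The concern.** A safety table by cohort is interpretable only if cohort membership is fixed before the safety outcome is known. Here one reason for being Day-0-only is the outcome itself, because a DLT stops the second dose. Applied literally, Sections 8.2 and 11.3.6 take the affected participant out of the cohort whose regimen is being judged, may fill the place with someone new, and add the event to a different group.

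Safety in each study group and the pharmacokinetics are the two primary objectives (Section 3.1), and both are summarised by cohort. With three to six participants per cohort, moving one person changes what the table shows. The receiving groups are also defined by a particular dose and electroporation (EP) setting, so adding people treated differently blurs the A1 and A2 summaries.

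**Working it through.** **1. The plan's interval method.** Section 11.3.1 specifies exact 90% Clopper-Pearson intervals. For x events in n, the lower limit is the 5% quantile of Beta(x, n−x+1), or 0 when x = 0, and the upper limit is the 95% quantile of Beta(x+1, n−x). With x = N × Pr, this gives a width of 0.694 for N = 6 and 0.361 for N = 24 at Pr = 0.5, the two figures in Section 11.4. All 24 cells of Table 6 are reproduced to three decimals. The table's title says 95%, but at 95% those two widths would be 0.764 and 0.418, so the cells are 90% widths.

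**2. One participant through the text.** A Cohort C participant has a DLT after Day 0 and before the Day 3 dose.
- Section 7.3: the second dose is withheld, so the participant is Day-0-only.
- Section 8.1: stopping the intervention is not leaving the study, so follow-up continues by default.
- Sections 8.2 and 11.3.6: analysed in A1 or A2, and may be replaced.
- Sections 11.2 and 4.2: analysed, and the DLT counted, in Cohort C.

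The last two lines cannot both be followed for the same safety table.

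**3. Effect of one such DLT, with no other events.** When x = 0 the upper limit is 1 − 0.05^(1/n), for example 1 − 0.05^(1/6) = 0.393. When x = 1 the lower limit is 1 − 0.95^(1/n), for example 1 − 0.95^(1/6) = 0.009.

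| Table row | Count | Rate | 90% CI |
|---|---|---|---|
| Cohort of 6, kept as enrolled | 1/6 | 16.7% | 0.9% to 58.2% |
| Same, replacement added and both counted | 1/7 | 14.3% | 0.7% to 52.1% |
| Same, moved out and replaced | 0/6 | 0% | 0% to 39.3% |
| Receiving group of 3, before | 0/3 | 0% | 0% to 63.2% |
| Receiving group, after | 1/4 | 25% | 1.3% to 75.1% |
| Cohort E (n = 5), kept as enrolled | 1/5 | 20% | 1.0% to 65.7% |
| Cohort E, moved out and replaced | 0/5 | 0% | 0% to 45.1% |

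**4. Does the receiving group match?** Day 0 exposure per dMAb from Table 2:

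| Cohort | Day 0 dose | Hylenex per injection | Volume | OpBlock | Against A1 and A2 |
|---|---|---|---|---|---|
| A1 | 0.5 mg | 68U | 0.5 mL | 0078 | – |
| A2 | 1 mg | 135U | 1 mL | 0078 | – |
| B | 0.5 mg | 66.5U | 0.5 mL | 0078 | close to A1 |
| C | 1 mg | 135U | 1 mL | 0078 | same as A2 |
| D | 0.25 mg | 34U | 0.25 mL | 0078 | below both |
| E | 2 mg | 75U | 0.70 mL | 0078 | above both: 2/1 = 2 times A2, 2/0.5 = 4 times A1 |
| F | 0.5 mg | 75U | 0.55 mL | 0070 | dose of A1, different EP setting |
| G | 0.5 mg | 75U | 0.55 mL | 0078 | close to A1 |

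The text does not say how A1 or A2 is chosen. By Day 0 dose, B goes to A1 (0.5 mg); by planned total dose it goes to A2 (1 mg).

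**The case against.** **Safeguards during the trial.** A DLT goes to the DSMB (Section 4.2), safety reviews after the first cover all enrolled participants, every DLT is reported to the FDA in an expedited manner (Section 10.13.2), and one stopping rule in Section 10.11 runs across cohorts. This stands. It confines the problem mainly to the descriptive summaries of an open-label trial without hypothesis tests.

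**Narrow conditions.** Replacement is optional, and regrouping applies only to those who want to continue. The DLT must precede the Day 3 dose: a later DLT stays in its cohort, and a Cohort G participant who stops after Day 3 is not covered. This stands as a limit on how often the conflict arises.

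**Grouping by exposure received.** A Day-0-only Cohort C participant received exactly the A2 regimen, and B and G come close to A1. That is a fair argument for a PK summary. It does not justify moving safety data, because the move can be triggered by the safety event.

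**Stronger readings that the documents do not support:**
- *That masking is certain.* Sections 11.2 and 4.2 state the opposite rule, so the outcome is unsettled.
- *That two DLTs in six could be reported as 0/6.* Under Section 4.2 more than one DLT in six already makes the dose not tolerated, and nothing provides for two replacements at such a dose to complete the cohort.
- *That events always move to a lower dose.* Cohort D would move to a higher one.
- *That the not-tolerated rule is weakened.* At the plan's 30% DLT rate, the chance of at least 2 DLTs in 6 is 1 − 0.7^6 − 6 × 0.3 × 0.7^5 = 0.580. If a share s of DLTs preceded Day 3 and those participants were removed and replaced, the rate would become 0.3(1 − s)/(1 − 0.3s), and the chance would fall to 0.450, 0.287, 0.108 or 0.000 for s of 25%, 50%, 75% or 100%. The protocol gives no value for s. More to the point, Section 4.2 counts by enrolled cohort, under which the figure stays at 0.580.

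**Conclusion.** The concern holds as an internal contradiction on a primary objective. Sections 8.2 and 11.3.6 prescribe a regrouping that can depend on the outcome, and Sections 11.2 and 4.2 prescribe analysis as enrolled. The text leaves open which governs the safety tables.

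The size is one row in a small table: 1/6 shown as 0/6, or 1/5 as 0/5 in Cohort E, with the upper 90% limit falling from 58.2% to 39.3% or from 65.7% to 45.1%. These figures assume a single DLT before the Day 3 dose, a participant who stays in the study and is replaced, no other events in either group, and tables that follow Sections 8.2 and 11.3.6. Escalation and real-time safety review are largely unaffected.

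Separately, and with or without a DLT, the receiving groups do not fit Cohorts D and E by dose or Cohort F by EP setting, so the rule would mix exposures in the A1 and A2 summaries.

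**What to change.** Reconcile Sections 8.2 and 11.3.6 with Sections 11.2 and 4.2 by stating that:
- safety and DLT data of every dosed participant are analysed in the cohort of enrolment;
- a participant whose later dose was withheld for an AE or DLT stays in that cohort's denominator, even if replaced;
- replacements are added to the cohort and do not substitute for the participant replaced;
- any pooling of Day-0-only participants with A1 or A2 is limited to a labelled supplementary PK summary, by dose and EP setting actually received, and only where these match.

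This changes no dosing, withholding or escalation rule. The cost is a rewording of one sentence in each of two sections, and some cohorts will show n+1 or n+2 in the safety tables.

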8.3 Lost To Follow-Up

A participant will be considered lost to follow-up if he or she fails to return for more than 2 scheduled visits and is unable to be contacted by the study site staff. The following actions must be taken if a participant fails to return to the clinic for a required study visit:

- The site will attempt to contact the participant and reschedule the missed visit immediately and counsel the participant on the importance of maintaining the assigned visit schedule and ascertain if the participant wishes to and/or should continue in the study.
- Before a participant is deemed lost to follow-up, the investigator or designee will make every effort to regain contact with the participant where possible, 3 telephone calls and, if necessary, a certified letter to the participant's last known mailing address or local equivalent methods. These contact attempts should be documented in the participant's medical record or study file.
- Should the participant continue to be unreachable, he or she will be considered to have withdrawn from the study with a primary reason of lost to follow-up.

9 STUDY ASSESSMENTS AND PROCEDURES

See [Table 3](#) for Schedule of Events showing study procedures and the times at which they are to be carried out.

9.1 Informed Consent

All participants must sign the informed consent prior to any trial related procedures are performed. The informed consent documentation must be in accordance with applicable regulations and GCP. Qualified trial personnel will meet with prospective trial participants, explain the trial, and provide them with an informed consent form (ICF) that describes the screening tests, eligibility criteria for entering the trial, trial dosing schedules and follow-up procedures, in a language understandable to the participant. Explanation of the trial includes, but is not limited to, trial objectives, potential benefits and risks, discomforts/inconveniences, and the participant's rights and responsibilities. The participant is then requested to sign and date the ICF. A copy of the signed informed consent documentation must be provided to the participant. The qualified trial personnel will document the process of obtaining informed consent within the source record. Signed ICFs are maintained in the participant's source records and must be accessible for verification at any time. Signing of the ICF begins the 30-day screening window.

The initial consent will be in person. Re-consenting may be conducted in-person or remotely. The participant and research team will review the amended consent form in detail and be provided with a clear and detailed explanation of the consent changes. The participant will have the opportunity to have all questions answered. If the participant must complete the consent form remotely, the consent form will be sent electronically. Participants will be required to either print, sign, and send a scanned copy of the consent form to the study team or send by mail. The study member(s) obtaining consent will sign the consent form and then provide a copy to the participants. Alternatively, if an MD investigator is unable to sign the consent form in person but able to re-consent remotely, the subject will sign the consent form

and study staff will provide them with a signed copy, when available. Obtaining re-consent signatures through DocuSign may also be an option. The re-consent process will be documented in PennChart.

9.2 Assignment of Participant Identification Numbers

Each participant who consents will be assigned a unique participant identification number (SID), which identifies the participant for all trial-related procedures. SIDs are a combination of a four-digit site code and a four-digit participant number starting with 0001. Once assigned, SIDs cannot be reused for any reason. Information regarding the SID and screen date will be documented on a screening and enrollment log/system and in the eCRF.

Participants meeting eligibility criteria listed in the protocol will be assigned by the site in accordance with the allocation schedule provided by the Sponsor ([name]).

9.3 Medical History

All relevant (as judged by the investigator) past and present conditions at screening, as well as prior surgical procedures will be recorded for the main body systems. Illnesses first occurring or detected after the signing of the informed consent, or during the study and/or worsening of an existing illness in severity, frequency or nature after signing of the informed consent are to be documented as AEs on the CRF. Prior treatments, defined as administered up to 8 weeks prior to the time of informed consent, should be recorded in the CRF as prior medications. Concomitant treatments, defined as continuing or new treatments taken at or after the signing of the informed consent, should be recorded in the CRF as concomitant medications.

9.4 Safety Evaluations

The following evaluations for safety will be performed.

9.4.1 Physical Exam and Targeted Physical Assessments

A full physical examination will be conducted during screening and at study discharge. A targeted physical assessment (physical exam focused on the area of specific symptoms) will be performed at other visits as determined by the Investigator or directed per participant complaints.

Injection Site Reaction

Injection site reaction assessed 30 minutes post injection and at all subsequent visits up to Day 10. Systemic and local reaction assessment consists of evaluation of the following:

Systemic: hypotension, hyperhidrosis, erythema, headache, dizziness, myalgia, arthralgia, fever, peripheral edema; and

Local reactions: pain, pruritus, erythema, swelling, scab, infection.

9.4.2 Vital Signs

Vital signs including oral temperature, respiration rate, blood pressure and heart rate will be measured at screening and all other in-person study visits. Vital signs will be performed both pre- and post-inoculation at Day 0, Day 3, Day 28, and/or Day 31 visits (as applicable).

9.4.3 Height, Weight, Handedness

Handedness will be recorded for each participant.

Weight (kg) and height (cm) will be collected at screening and at study discharge.

9.4.4 12-lead ECG

A single 12-lead ECG will be performed at screening, at pre- and post-dosing on Days 0, 3, 28, and 31 (as applicable to each cohort), and at each study visit. The ECG should include measurements of ventricular rate, PR, QRS, QT, and QTc, as well as an assessment of whether the ECG is normal or abnormal. Abnormal ECGs should be interpreted as clinically significant or not clinically significant. For Cohorts Expansion, if applicable, further dosing should be delayed in the event of a clinically significant abnormal post-dose ECG result from Day 0 until it has been reviewed by the PI, qualified PI designee, Medical Director, or Sponsor consultant cardiologist and deemed safe to proceed.

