9.5 Injection and Electroporation (EP)

Injections of investigational product are immediately followed by electroporation. Participants in Cohorts A1 and A2 will receive two injections of dMAb AZD5396 and dMAb AZD8076 in the deltoid/quadriceps followed immediately by EP on Day 0. Cohorts B-G will receive two injections of dMAb AZD5396 and dMAb AZD8076 in the deltoid/quadriceps followed immediately by EP on both Days 0 and 3, for a total of 4 injections. Cohort G will also receive two injections of dMAb AZD5396 and dMAb AZD8076 in the deltoid/quadriceps followed immediately by EP on Days 28 and 31, for a total of 8 injections. If preferred or needed, both doses can be done in the deltoid region or the lateral quadriceps on Days 0, 3, 28, and/or 31.

Study Agent must not be given within 2 cm of a tattoo, scar, or active lesion/rash. Also, IM injection followed immediately by EP must not be performed in the muscle of an extremity which has any metal hardware (e.g., surgical rods, pins or joint replacements). The two injections on Days 0, 3, 28, and/or 31 will be given on the same side deltoid and lateral quadriceps (i.e., left side or right side of the body). If preferred or needed, both doses can be done in the deltoid region or the lateral quadriceps.

The side-port needle should be inserted fully with firm pressure until injection is completed, then wait for a few seconds and then removed. Training on this method of injection will be provided.

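### The ECG dosing hold in Protocol section 9.4.4 names an undefined group and only the Day 0 ECG, so Cohort G's Day 3 and Day 28 post-dose ECGs trigger no stated hold

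*Protocol*

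**What the plan says.** Section 9.4.4 schedules a 12-lead ECG "at pre- and post-dosing on Days 0, 3, 28, and 31 (as applicable to each cohort"), as well as at screening and at each study visit. It also fixes how a tracing is read: "Abnormal ECGs should be interpreted as clinically significant or not clinically significant". It then states one dosing consequence: "For Cohorts Expansion, if applicable, further dosing should be delayed in the event of a clinically significant abnormal post-dose ECG result from Day 0". The delay lasts until one of the named reviewers clears it; these are the principal investigator or a qualified designee, the Medical Director, and a cardiologist consulting for the sponsor.

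The cohorts defined in section 4.1 and Table 2 are A1, A2 and B to G. A1 and A2 are dosed on Day 0 only, B to F on Days 0 and 3, and G on Days 0, 3, 28 and 31. Section 9.5 confirms the extra Cohort G dosing: "followed immediately by EP on Days 28 and 31, for a total of 8 injections". The nearest text to an expansion cohort is the justification for opening new cohorts in section 4.1, "By expanding the cohorts, we will gather a larger sample size", which does not say which cohorts it means.

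**The concern.** A site following section 9.4.4 has to answer two questions: which participants the hold covers, and which ECGs trigger it. The first cannot be answered from the document, because the group is never defined. The second has a clear answer that looks too narrow: the hold is tied to Day 0, while the ECG schedule in the same paragraph runs to Day 31.

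Cohort G is the only cohort dosed after Day 3, and sections 4.1 and 4.2 exempt it from the 14-day waiting period. If one of its participants has a clinically significant post-dose tracing on Day 3 or Day 28, the protocol gives no explicit instruction to delay the next dose. What is lost is that instruction. Clinical judgement remains, since the principal investigator or a designee could release the hold alone. No endpoint or escalation decision is affected.

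**Working it through.** **Check on the dosing schedule.** Two injections per dosing day × 4 dosing days = 8 injections per Cohort G participant, which reproduces the total in section 9.5.

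**Inputs.** Planned evaluable participants from the rows of Table 2: B 6, C 6, D 6, E 5, F 5, G 5. Dosing days are from section 4.1.

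**Dosing visits after Day 0.**
- Day 3, Cohorts B to G: 6 + 6 + 6 + 5 + 5 + 5 = 33
- Day 28, Cohort G: 5
- Day 31, Cohort G: 5
- Total: 33 + 5 + 5 = 43, of which Cohort G has 5 + 5 + 5 = 15

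**Visits for which the preceding dosing day's ECG triggers the hold.** A visit counts as covered if its cohort is in the named group and the preceding dosing day is Day 0. Only Day 3 visits can meet this.

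| Meaning given to the undefined group | Covered | Not covered |
|---|---|---|
| B to G | 33 | 43 − 33 = 10 |
| D to G | 6 + 5 + 5 + 5 = 21 | 43 − 21 = 22 |
| E to G | 5 + 5 + 5 = 15 | 43 − 15 = 28 |
| No identifiable cohort | 0 | 43 |

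On the B to G reading, the 10 are the Day 28 visits (which follow the Day 3 ECG) and the Day 31 visits (which follow the Day 28 ECG). That is 10 of Cohort G's 15 later visits, or 10 × 2 = 20 injections.

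**How much time and ECG review lies in between.** Table 4 gives four ECG visits between the Day 3 and Day 28 doses: Days 7 and 10, and Weeks 2 and 3. It gives none between Day 28 and Day 31. Section 7.2 says "Visit dates and windows must be calculated from Day 0", and both visits have ±1 day windows. Day 28 therefore falls on Days 27 to 29 and Day 31 on Days 30 to 32. The shortest gap is 30 − 29 = 1 day, the longest 32 − 27 = 5 days, and the nominal gap 3 days.

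**Whether another provision supplies the hold.**
- Section 7.3: "If a participant has a DLT, as outlined in the protocol, the second dose of the product will not be given". This requires a DLT, and its consequence is worded for a second dose, not for the third or fourth.
- Section 10.10: the systemic and laboratory DLT criteria need a related event of Grade 3 or above. Section 10.9 lists ECG among laboratory abnormalities, but Appendix B has no rows for PR, QRS or QTc. It grades heart rate and, in general terms, illness or clinical adverse events.
- Sections 8.1 and 8.2: the investigator may change management or withdraw a participant, but no delay is stated.
- Section 10.11: the trial pauses for SAEs, potentially life-threatening events, unexpected Grade 4 toxicities, anaphylaxis, clustered Grade 3 or higher events, or DLTs in two thirds of a cohort.

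A clinically significant ECG below these thresholds is left to discretion.

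**Pre-dose ECG.** Section 9.4.4 requires one on every dosing day, and Table 4 marks an ECG on each. The pre-dose list in section 7.3 omits it. This is an inconsistency between sections.

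**The case against.** The strongest reply is that the missing words would change little. The hold is advisory in tone and can be released by the investigator or a designee, who under section 8.1 already decides on management after any clinically significant finding. A Day 0 abnormality would delay all further dosing, including Days 28 and 31. Section 10.9 makes the Medical Director responsible for safety monitoring and names ECG. Section 8.2 allows withdrawal, including for a newly developed exclusion criterion, and any cardiovascular disease is one. Section 7.3 requires an hour's observation and no discharge until vital signs are normal or back to baseline. Entry requires a screening ECG without clinically significant findings. All of this stands, and it is why the importance is minor. None of it is a stated delay triggered by the Day 3 or Day 28 tracing.

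One could also read the trigger as Day 0 onward. That is strained: the later word introducing the review completes the delay, not the date.

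Two stronger conclusions are tempting and are not supported. A reader might infer that ten Cohort G dosing visits go ahead without cardiac review. They do not: the Day 28 doses follow four ECG visits, every abnormal tracing must be classified, and a pre-dose ECG is required. A reader might also infer from the section 7.3 list that no pre-dose ECG is done on Day 31. Section 9.4.4 expressly requires it, and an incomplete list does not cancel that.

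**Conclusion.** The point holds as a scope error in a participant-safety rule that the protocol chose to state. The group is undefined under any reading, and the trigger omits Cohort G's Day 3 and Day 28 post-dose ECGs. The size is 10 of 43 later dosing visits on the most favourable reading and 22, 28 or 43 on narrower ones; the practical gap is mainly the 5 Day 31 visits. Importance is minor.

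The counts assume the planned evaluable numbers in Table 2; replacements or partial dosing would shift them. They count visits the rule would govern. They are not expected events, and the protocol gives no rate of clinically significant ECGs. Only the sponsor can say which cohorts were meant.

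**What to change.** In section 9.4.4, replace the undefined group with the named repeat-dose cohorts (B to G, or those the sponsor intended, including G). Replace the Day 0 trigger with a clinically significant abnormal post-dose ECG from any prior dosing day (Day 0, 3 or 28, as applicable). Keep the reviewers already named. With B to G named, none of the 43 later visits would lack the hold.

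For consistency, add the pre-dose 12-lead ECG to the section 7.3 pre-dose list.

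The cost is one reworded sentence and one added bullet. No ECG is added beyond those section 9.4.4 already requires. The downside is an occasional dose delayed beyond its ±1 day window.
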